### 6.3.2 Rationale for Concomitant Antihistamine Dose and Regimen

The target population for this study comprises CU subjects who remain symptomatic despite treatment with AH therapy alone (at approved doses). The updated International Guideline on definition, classification, diagnosis, and management of urticaria (Zuberbier, 2014), evidence-based recommendations by an international expert team, has led to a treatment algorithm that recommends as Step 1 and Step 2 the use of non-sedating AHs at approved, or increased doses (up to 4-fold), respectively. As Step 3, the addition of omalizumab, cyclosporin A, or montelukast (LTRA) is recommended. None of the therapeutic recommendations of Step 2–3 are currently licensed for subjects with CINDU, including CholU and UF; therefore, to reflect the most current treatment algorithm for CINDU subjects, this study allows use of AH (at approved doses) as background medication.

### 6.4 Risks and Benefits

The inclusion and exclusion criteria are selected to enroll subjects with CU most likely to benefit from participating in the study. The overall risk will be minimized by compliance with the inclusion/exclusion criteria, close clinical monitoring including the use of a diary to monitor symptoms, and the use of rescue medication. See the Investigator Brochure for the complete safety summary of AK002.

The long-term continuation treatment will provide the option of an additional 12 months of treatment for patients with severe disease at baseline who recorded a complete response while on treatment with AK002 (1 mg/kg or 3 mg/kg) and who developed severe symptoms within 6 months of discontinuing AK002. The continuation protocol will be limited to patients who have no other treatment options, that is CholU, UF, or Xolair failures in patients with CSU.

The Investigator will provide the patient with written instructions to contact them if symptoms of CU worsen. Investigators will be instructed on acceptable treatments for worsening CU, which will allow subjects to continue on the study. The clinical benefits and safety profile of AK002 in subjects with CU has not yet been established. The risk for subjects participating in this study includes the potential for known safety issues, such as hypersensitivity reactions including anaphylaxis (Appendix 1), as well as for any unknown safety effects that could occur.

## 7. Population

The study population will be comprised of approximately 48 adult subjects ( $\geq 18$  and  $\leq 85$  years old) with the diagnosis of CU. Approximately 12 subjects of each subgroup of CU (CholU, UF, CSU-XOLAIR® (omalizumab) naïve, CSU-XOLAIR® (omalizumab) failures) will be recruited. Subjects with acute urticaria will be excluded.

Approximately 48 subjects enrolled at approximately 4 study centers in the USA and Germany are expected to participate in the study.

### **7.1 Rationale for the Number of Subjects**

The planned sample size of approximately 48 subjects is based on common practice in early phase, proof-of-concept studies.

### **7.2 Inclusion/Exclusion Criteria**

The Investigator must ensure that all subjects meet the following inclusion criteria and none of the exclusion criteria.

#### **7.2.1 Inclusion Criteria**

- 1) Adults ( $\geq 18$  and  $\leq 85$  years old)
- 2) Body weight  $< 125$  Kg
- 3) Informed consent signed and dated
- 4) Able to read, understand, and willing to sign the informed consent form and comply with study procedures
- 5) Diagnosis of CU for at least three months, refractory to antihistamine treatment in single or 4-fold dosage
- 6) Willing, committed, and able to return for all clinic visits and complete all study-related procedures, including willingness to have IV infusion of study drug administered by a qualified person
- 7) Females of childbearing potential must have a negative pregnancy test at Baseline. Female subjects must be willing to use highly effective contraception (Pearl-4 Index  $< 1$ ) or abstain from sexual activity from Screening until the end of the study, or for 120 days following the last dose of study drug, whichever is longer. A woman will be considered not of childbearing potential if she is post-menopausal for greater than two years (FSH  $> 40$  mL) or surgically sterile (bilateral tubal ligation, bilateral oophorectomy, or hysterectomy).

Male patients with female partners of childbearing potential must agree to use a highly effective method of contraception from Screening until the end of the study or for 120 days following the last dose of study drug, whichever is longer. All fertile men with female partners of childbearing potential should be instructed to contact the Investigator immediately if they suspect their partner might be pregnant (e.g., missed or late menstrual period) at any time during study participation.

- 8) No participation in other clinical trials 4 weeks before participation in this study
- 9) Uncontrolled CU (UCT <12) at the time of enrollment
- 10) For extended dosing, subjects must have a baseline (Day 1) UCT of  $\leq 5$  and a week 22 (Day 155) UCT of  $\geq 12$  (Complete Response). They must have a UCT of  $\leq 5$  between Day 155 and Day 309 (i.e., within 6 months from last dose).

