## 5. Endpoints

### 5.1 Primary Endpoint

The primary endpoint is the change in Urticaria Control Test (UCT), a score for symptom control in chronic urticaria, from Day 1 (baseline) to Week 22 in CU subjects after treatment with AK002. At Baseline, a 4-week recall will be recorded, prior to first study drug administration. A change of the UCT score of 3 or more points is regarded as clinically relevant (minimal clinically important difference [MCID]).

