#### 6.1.1 Screening Period

At the beginning of the screening period, eligible subjects will be asked to sign the informed consent form (ICF) and their current medication will be discussed. During the screening period, subjects will continue with their current antihistamine medication (approved dose). Subjects who do not meet all eligibility criteria at Screening, or who qualify at Screening but are not enrolled, may be assigned a new Patient ID number and re-screened once. Subjects re-screened within

30 days of signing the initial consent will not need to sign a new ICF providing there have been no changes to the ICF. A patient is considered enrolled in the trial when the patient receives their first dose of AK002.

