**Table 3 Notes**

- Subjects who do not meet all eligibility criteria at Screening, or who qualify at Screening but are not enrolled, may be assigned a new Patient ID number and re-screened once. Subjects re-screened within 30 days of signing the initial consent will not need to sign a new ICF providing there have been no changes to the ICF.
- Baseline is defined as up to 48 hours prior to first dose.
- AK002 will be administered as a single peripheral IV infusion. Please refer to the Pharmacy Manual for detailed instructions on preparations, administration, and infusion rate.
- Subjects should complete the [REDACTED] on a weekly basis. On weeks where a clinic visit is not scheduled, the [REDACTED] should be completed at home.

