### **13. Data Analysis**

This section outlines the statistical methods to be used for the analysis of the data from the study. A separate Statistical Analysis Plan (SAP), which will be completed and signed off prior to data base lock.

When the SAP differs from analyses described in the protocol, the SAP will take precedence.

Continuous variables will be summarized using number of non-missing observations, mean, standard deviation (SD), median, minimum, and maximum; categorical variables will be summarized using the frequency count and the percentage of subjects in each category.

Baseline for data analysis is defined as the last assessment prior to the first infusion of the study drug.

The primary summaries will be based on individual cohorts and the data from all 3 cohorts combined, wherever possible.

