3.9.9 Prior, Concomitant, and Prohibited Medications

Prior medications and concomitant medications will be extracted from the Prior/Concomitant Medication CRF. Medications taken prior to Study Day 1 will be considered as prior medications and medications taken on or after Study Day 1 will be considered as concomitant medications. Prior and concomitant medications will be coded using WHO Drug Dictionary (WHODD March 2018 release) for Preferred Term (PT) and Anatomical Therapeutic Chemistry (ATC) classification.

Prohibited medications include, but are not limited to,

- Omalizumab
- H2-antihistamines
- Routine (daily or every other day during 5 or more consecutive days) doses of systemic corticosteroids
- Routine (daily or every other day during 5 or more consecutive days) doses of systemic hydroxychloroquine
- Routine (daily or every other day during 5 or more consecutive days) doses of methotrexate, cyclosporine A, cyclophosphamide, tacrolimus and mycophenolate mofetil
- Intravenous immunoglobulin G
- Plasmapheresis
- Regular (daily or every other day) doxepin (oral)
- Inactive vaccination
- Live attenuated vaccine
- Leukotriene Antagonists

4. Definitions

Table 4 Terminology and Definition

Terminology	Definition
Study Medication/Drug (SM)	AK002 administered by IV infusion.
Study Day	The first dose date (Day 1) is defined as the date on which a subject took the first dose of study medication (SM). Other study days are defined relative to Study Day 1. For visits prior to the first dose of the SM, Study Day is calculated as Visit Date – Day 1. For visits after the first dose, Study Day is calculated as Visit Date – Day 1 +1.
Enrolled	Subject who has signed informed consent, met all eligibility criteria at Screening, and having received the first dose of the study drug.
Completer for the Study	Subject who completes End of Study visit
Baseline	Baseline is defined as the non-missing value collected most recent to and before the time of the very first dose of the SM.
Prior Medication	Medication collected on the Prior/Concomitant Medication CRF, with start date prior to Study Day 1.
Concomitant Medication	Medication collected on the Prior/Concomitant Medication CRF, with end date on/after Study Day 1.
Treatment-emergent	Adverse events with onset date on or after the start of first study drug administration.

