7.1 Analysis Populations

The population of “all enrolled subjects” consists of all subjects who signed informed consent, met all eligibility criteria at Screening, and having received the first dose of the study drug.

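### The only scheduled pre-dose UCT is both the entry test and the baseline of the primary change, which builds in a modest upward regression to the mean

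*Protocol*

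**What the plan says.** **Entry test.** Protocol 7.2.1 no. 9: "Uncontrolled CU (UCT <12) at the time of enrollment". Protocol 6.1.1 fixes when that is: "A patient is considered enrolled in the trial when the patient receives their first dose of AK002".

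**First UCT.** The UCT row of Protocol Table 3 and of SAP Table 1 is blank at Visit 1 (Day -28) and starts at Visit 2 (Day 1). Eligibility is confirmed at Visit 2, and the Table 3 notes set the window: "Baseline is defined as up to 48 hours prior to first dose".

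**Baseline.** Protocol 5.1 defines the primary change "from Day 1 (baseline) to Week 22 in CU subjects after treatment with AK002" and adds: "At Baseline, a 4-week recall will be recorded, prior to first study drug administration". Protocol 13 says: "Baseline for data analysis is defined as the last assessment prior to the first infusion of the study drug". SAP Section 4 (Table 4) agrees: "Baseline is defined as the non-missing value collected most recent to and before the time of the very first dose of the SM". SAP 5.1 uses Week 10 in place of Week 22 for subjects enrolled under Amendment 2.1, with the same Day 1 baseline.

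**Analysis.** All subjects receive AK002 (SAP 3.3). There are no hypothesis tests (SAP 3.5) and no covariate adjustment (SAP 6.3). The mean change is reported by cohort with a 95% CI (SAP 7.7.1).

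**Timing of eligibility in the SAP.** SAP 7.1 describes enrolled subjects as having "met all eligibility criteria at Screening, and having received the first dose of the study drug". SAP Section 4 and 7.1.2 (Safety population) say the same. No UCT is scheduled at the Screening visit.

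**The concern.** When one noisy score decides entry and is then the starting point of the change, subjects who happen to score low that day are kept and those who happen to score high are turned away. On re-measurement the retained group's mean rises even if nothing has been done. A control arm would show the same rise and cancel it, but this trial has none. The shift always favours the drug, and a larger sample does not shrink it.

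It enters the primary endpoint and the UCT responder rates of SAP 5.2: clinically meaningful response (CMR, a gain of at least 3) and complete response (CR, a score of at least 12 with a gain of at least 3). Without a comparator these figures are the efficacy evidence available for deciding whether to pursue the randomized trial mentioned in Protocol 3. Neither document mentions the effect.

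**Working it through.** **No figure to reproduce.** The sample size is set by convention, and the plan gives no UCT mean, SD, reliability or expected change.

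**Inputs from the documents.** Entry cut UCT <12 (Protocol 7.2.1); integer scores 0–16 (Protocol 10.4.2); MCID 3 points (Protocol 5.1); CR and CMR (SAP Section 4); about 12 subjects per cohort (SAP 3.3).

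**Assumptions, not in the documents.** UCT before selection is roughly normal with mean 6–10 and SD 3.5–4; correlation ρ between Day 1 and the later score is 0.6–0.8; no drug effect, placebo response or trend.

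**Step 1: gate and baseline on the same score.** Expected spurious gain = (1 − ρ) × SD × φ(a)/Φ(a), with a = (11.5 − mean)/SD, because a score of 11 or less qualifies.

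| Case | Mean | SD | ρ | a | φ(a)/Φ(a) | Gain |
|---|---|---|---|---|---|---|
| Low | 6 | 3.5 | 0.8 | 1.571 | 0.1161/0.9420 = 0.123 | 0.2 × 3.5 × 0.123 = 0.09 |
| Middle | 8 | 4 | 0.7 | 0.875 | 0.2721/0.8092 = 0.336 | 0.3 × 4 × 0.336 = 0.40 |
| High | 10 | 4 | 0.6 | 0.375 | 0.3719/0.6462 = 0.576 | 0.4 × 4 × 0.576 = 0.92 |

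Simulation with scores rounded and clipped to 0–16 (2,000,000 subjects per case) agrees; the middle case is 0.41. Widening the ranges to SD 3–4 and ρ 0.5–0.8 gives 0.05 to 1.15.

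**Step 2: responder rates with no drug effect** (simulation, middle case).

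| | Baseline is the gating score | Baseline is a separate score |
|---|---|---|
| CMR | 23.8% | 20.5% |
| CR | 7.7% | 5.2% |

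Selection adds 23.8 − 20.5 = 3.3 percentage points to CMR. Over the range it adds from just under 1 (rate 13%) to about 8 (32% against 24%). In the middle case 20.5/23.8 = 86% of chance CMR is ordinary fluctuation.

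**Step 3: scale.** The middle gain is 0.41/3 = 14% of the MCID. At n = 12 the 95% CI half-width is 2.201 × SD/√12: 1.9 points for an assumed SD of change of 3, and 2.5 for 4.

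**Step 4: what an added Visit 1 score would do, keeping the Day 1 gate.**
- *Visit 1 as baseline.* Expected change = (ρ[Visit 1, Day 1] − ρ[Day 1, Week 22]) × SD × φ(a)/Φ(a). With equal correlations this is 0. If correlation decays with time, part of the bias stays. For example, with a Visit 1–Day 1 correlation halfway between 0.7 and 1, (0.85 − 0.70) × 4 × 0.336 = 0.20, half of the middle case.
- *Mean of Visit 1 and Day 1 as baseline.* (0 + 0.40)/2 = 0.20, so half remains even with equal correlations.
- *Visit 1 to Day 1 change.* Selection on Day 1 pulls it to about −0.40 in the middle case. If Visit 1 were the gate instead, it would be about +0.40. It carries the selection effect either way.

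**The case against.** **Size and purpose.** The study is a descriptive pilot with no tests, and a controlled trial would follow only if the indication is pursued. The middle-case shift of 0.4 points is small beside a half-width of 1.9–2.5 points in a cohort of 12. The high case needs a source mean of 10, where about 35% (1 − 0.646) would fail the gate; that sits poorly with a population already required to be antihistamine-refractory. This stands, and it makes the point one of bias in an estimate, modest in size, not of error rates.

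**The qualifying score is inferred.** The documents never say outright that the Day 1 UCT is the qualifying one; this follows from the schedule and the definition of enrolment. If sites took an unscheduled UCT during screening, the overlap would be smaller. A reader might infer from the SAP wording that the criterion cannot be satisfied at all. The documents do not support that: screening is a four-week period and eligibility is confirmed at Visit 2. What they show is a conflict of wording.

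**Other pre-dose data exist.** The diary runs from Visit 1. It gives symptom data before dosing, but not the UCT on which the primary endpoint rests.

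**Moving the gate to Visit 1 would be costly.** About 3–21% of subjects would then be dosed with a Day 1 UCT of 12 or more, which both documents call well controlled. This stands as an argument against changing the entry criterion. It does not count against collecting the score.

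**Enrolled subjects.** The SAP refers to subjects enrolled under earlier amendments, for whom no Visit 1 UCT was scheduled. This also stands.

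**Conclusion.** The point holds in a limited form. By the schedule, one UCT serves as entry gate and as primary baseline, and with no comparator the mean change is shifted towards benefit. Under the stated assumptions the shift is about 0.09 to 0.92 points, with 0.41 in the middle, and CMR is inflated by about 1 to 8 percentage points. The direction follows from the design whenever UCT varies within a subject; the size rests wholly on assumed figures.

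Two stronger readings are not supported. A reader might infer that a clinically relevant mean gain could be an artefact of selection; the shift stays well below 3 points, and most chance CMR is ordinary fluctuation that no choice of baseline removes. A reader might also infer that a Visit 1 score would supply an untreated control through the Visit 1 to Day 1 change; that change carries the selection effect itself. Placebo response and natural course remain unaddressed in either case.

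**What to change.** 1. Add the four-item UCT at Visit 1 in Protocol Table 3 and SAP Table 1. Leave the Day 1 entry criterion and the primary baseline unchanged.
2. Add to SAP 7.7.1 a sensitivity analysis of the UCT change, CR and CMR with the Visit 1 score, not used for selection, as baseline. State that its expected no-effect mean change is about 0 only if the correlation is constant over time, and that otherwise it removes part of the bias. Responder rates need not fall in that case, because scores further apart fluctuate more. An average of Visit 1 and Day 1 is a weaker choice.
3. Do not present the Visit 1 to Day 1 change as an unbiased estimate of change without AK002, and do not subtract it from the primary result.
4. For subjects enrolled without a Visit 1 UCT, state the limitation in the SAP and the study report.
5. Reconcile the Screening wording in SAP Section 4, 7.1 and 7.1.2 with the schedule, and say which UCT qualifies a subject.

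**Cost.** One short questionnaire at an existing visit, one extra table, and possibly a slightly smaller change in the sensitivity analysis. About 3–21% of subjects would have a Visit 1 UCT of 12 or more under the same assumptions with constant correlation, and those at 14 or above cannot gain 3 points. The table should show these counts. The screening period and the UCT recall are both four weeks, so no visit has to be added.

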### **7.2.2 Exclusion Criteria**

- 1) Acute urticaria
- 2) Concurrent/ongoing treatment with immunosuppressives (e.g., cyclosporine, methotrexate, dapsone, or others) within 4 weeks or 5 half-lives prior to Baseline, whichever is longer
- 3) Significant medical condition rendering the patient immunocompromised or not suitable for a clinical trial
- 4) Significant concomitant illness that would adversely affect the subject's participation or evaluation in this study
- 5) History of malignancies within five years prior to screening other than a successfully treated non-metastatic cutaneous, basal, or squamous cell carcinoma and/or in situ cancer
- 6) Presence of clinically significant laboratory abnormalities
- 7) Lactating women or pregnant women
- 8) Substance abuse (drug or alcohol) or any other factor (e.g., serious psychiatric condition) within the last 5 years that could limit the subject's ability to comply with study procedures
- 9) Subjects who are detained officially or legally to an official institute or those that have been committed to an institution by virtue of an order issued either by the judicial or the administrative authorities will be excluded
- 10) Use of omalizumab within the last 2 months
- 11) Receipt of intravenous IgG therapy 30 days prior to Baseline
- 12) Plasmapheresis 30 days prior to Baseline
- 13) Use (daily or every other day) of Doxepin 14 days prior to Baseline
- 14) Receipt of inactive vaccination or live attenuated vaccine 30 days prior to Baseline
- 15) Use of H2-antihistamines 7 days before Baseline

- 16) Intake of leukotriene antagonists within 7 days prior to enrollment
- 17) Intake of systemic corticosteroids (e.g., oral or depot) within 14 days prior to enrollment
- 18) Positive screening for ova and parasite test at Baseline
- 19) Treatment of helminthic parasite within 6 months of screening
- 20) Positive HIV serology at screening
- 21) Positive Hepatitis serology at baseline, except for vaccinated patients or patients with past but resolved hepatitis at screening
- 22) Donation or loss of >500 mL of blood within 56 days prior to administration of study drug or donation of plasma within 7 days prior to administration of drug
- 23) Known hypersensitivity to any ingredients of AK002 or drugs related to AK002 (e.g., monoclonal antibodies, polyclonal gammaglobulin)

## **8. Study Treatment**

### **8.1 Investigational Treatment**

AK002 will be administered as an intravenous (IV) infusion at a dose of 0.3 mg/kg given over a period of approximately 4 hours on Study Day 1. If well tolerated, dose will be increased to 1 mg/kg, given over a period of approximately 4 hours on study Day 29 and Day 57 ( $\pm 2$  days). Dose will be increased to 3 mg/kg on Days 85, 113, and 141 ( $\pm 2$  days) if the UCT score is <12 and/ or at the discretion of the Investigator in consultation with the Allakos Medical Monitor. If the UCT score  $\geq 12$ , and if the Investigator in consultation with the medical monitor feels that the patient has received adequate symptom improvement, patient will remain at the 1 mg/kg dose. All doses will be given over a period of approximately 4 hours. The duration of infusion and the rate at which the infusion is given may be adjusted based on Investigator discretion.

The amount of AK002 to be administered will be calculated based on the patient's body weight determined within 24 hours of each infusion.

### **8.2 Concomitant Treatment**

One hour prior to dosing with AK002, subjects will receive pre-treatment oral doses of acetaminophen/paracetamol (1000 mg) and cetirizine (10 mg) for doses 1 and 2. Any premedication for subsequent doses will be based on the Investigator's discretion.

Subjects will be treated with a standard dose of second-generation AH (once per day) or up to a 4-fold dose of second-generation AH (standard of care) with dose and regimen established during Screening. In the event of symptom resolution during the study, the dose and schedule of AH treatment established during screening must be continued throughout the study.

